11.9 Interim analyses

Commercially Confidential Information

12 Ethical considerations

12.1 Regulatory and ethical compliance

This clinical study was designed and shall be implemented, executed and reported in accordance with the ICH Harmonized Tripartite Guidelines for Good Clinical Practice, with applicable local regulations (including European Directive 2001/20/EC, US Code of Federal Regulations Title 21, and Japanese Ministry of Health, Labor, and Welfare), and with the ethical principles laid down in the Declaration of Helsinki.

12.2 Responsibilities of the investigator and IRB/IEC

Before initiating a trial, the investigator/institution must obtain approval/favorable opinion from the Institutional Review Board/Independent Ethics Committee (IRB/IEC) for the trial protocol, written informed consent form, consent form updates, subject recruitment procedures (e.g. advertisements) and any other written information to be provided to subjects. Prior to study start, the investigator is required to sign a protocol signature page confirming his/her agreement to conduct the study in accordance with these documents and all of the instructions and procedures found in this protocol and to give access to all relevant data and records to Novartis monitors, auditors, Novartis Quality Assurance representatives, designated agents of Novartis, IRBs/IECs, and regulatory authorities as required. If an inspection of the clinical site is requested by a regulatory authority, the investigator must inform Novartis immediately that this request has been made.

For multi-center trials, a Coordinating Investigator will be selected by Novartis by the time of Last Patient Last Visit to be a reviewer and signatory for the clinical study report.

12.3 Publication of study protocol and results

The key design elements of this protocol will be posted in a publicly accessible database such as clinicaltrials.gov. In addition, upon study completion and finalization of the study report the results of this trial will be either submitted for publication and/or posted in a publicly accessible database of clinical trial results.

12.4 Quality control and quality assurance

Novartis maintains a robust Quality Management (QM) system that includes all activities involved in quality assurance and quality control, including the assignment of roles and responsibilities, the reporting of results, and the documentation of actions and escalation of issues identified during the review of quality metrics, incidents, audits and inspections.

Audits of investigator sites, vendors, and Novartis systems are performed or overseen by Novartis Pharma Auditing and Compliance Quality Assurance (or CRO working on behalf of Novartis), a group independent from those involved in conducting, monitoring or performing quality control of the clinical trial. The clinical audit process uses a knowledge/risk based approach.

Audits are conducted to assess GCP compliance with global and local regulatory requirements, protocols and internal SOPs, and are performed according to written Novartis processes.

13 Protocol adherence

This protocol defines the study objectives, the study procedures and the data to be collected on study participants. Additional assessments required to ensure safety of subjects should be administered as deemed necessary on a case by case basis. Under no circumstances is an investigator allowed to collect additional data or conduct any additional procedures for any research related purpose involving any investigational drugs under the protocol.

Investigators ascertain they will apply due diligence to avoid protocol deviations. If an investigator feels a protocol deviation would improve the conduct of the study this must be considered a protocol amendment, and unless such an amendment is agreed upon by Novartis and approved by the IRB/IEC and health authorities, where required, it cannot be implemented.

1.1 Scope of document

The RAP documents contain detailed information to aid the production of Statistics & Programming input into the Clinical Study Report (CSR) for trial “CAIN457X2201”.

The Statistical analysis plan (SAP) describes the implementation of the statistical analysis planned in the protocol.

1.2 Study reference documentation

This Statistical Analysis Plan is based on the protocol version 02 incorporating Amendment 02 dated 13Mar2018.

1.3 Study objectives

1.3.1 Primary Objective

- To assess the efficacy of secukinumab 300 mg subcutaneous (s.c.) vs. placebo in patients with overuse rotator cuff tendinopathy in relieving clinical symptoms at week 14.

1.3.2 Secondary Objectives

- To assess the efficacy of secukinumab 300 mg s.c. vs. placebo in patients with overuse rotator cuff tendinopathy in relieving symptoms over time.
- To assess the structural changes in the rotator cuff tendinopathy over time.
- To assess PK/immunogenicity in secukinumab treated patients.
- To confirm the safety and tolerability of secukinumab in patients with overuse rotator cuff tendinopathy over time.

1.3.3 Exploratory Objectives

Commercially Confidential Information

Commercially Confidential Information

1.4 Study design and treatment

This is a randomized, double-blind, placebo-controlled, multi-center, Phase II study of s.c. secukinumab 300 mg in approximately 100 randomized patients with overuse rotator-cuff tendinopathy without systemic inflammatory disease and refractory to SAIDs/acetaminophen, physiotherapy or corticosteroids. The patient and investigator will be blinded throughout the study, while the sponsor will be blinded until after the analysis of the primary endpoint. The study consists of a 4-week screening period, a 2-week run-in period, a 12-week treatment period and a 12-week follow-up period after last treatment ([Figure 1-1](#)).

The population will consist of patients with MRI-positive unilateral overuse (non-systemic inflammatory) shoulder tendinopathy, 18 - 65 years of age. Symptoms should have been present for at least 6 weeks but not more than 12 months. The tendinopathy must have been refractory to NSAIDS/acetaminophen as defined in the inclusion criteria. On MRI, patients may have no tendon tear or a partial tendon tear (up to 50% thickness, in max. 50% of patients). The patients should also have had at least 2 weeks of a standardized physiotherapy treatment.

[figure not shown]
The screening period will be used to assess eligibility and to start/continue patients on physiotherapy. In the run-in period the patient should have 2 weeks of stable NSAID/acetaminophen intake and standardized physiotherapy (defined in the SOM). Patients who meet the eligibility criteria at screening after the run-in period will go through baseline evaluations.

Eligible patients as per inclusion/exclusion criteria will be randomized to one of the two treatment arms: 7 s.c. injections of secukinumab 300 mg or placebo in a 12-week treatment period, followed by a 12-week follow-up period. Randomization will be stratified by the following 2 factors: Partial tear/no tear and previous steroid injection (yes/no), in order to achieve approximate balance between these factors in the treatment groups. The assessments to address the primary endpoint will be performed at 14 weeks (2 weeks after the last injection).

Patients will come to the out-patient clinic approximately 2-4 hours prior to dosing for the evaluations. Dosing will be on-site, except for injections at 1 and 3 weeks, that can be done either on site or by a nurse at the patient's home.

Safety assessments will include physical examinations, ECGs, vital signs, standard clinical laboratory evaluations (hematology, blood chemistry, and urinalysis), adverse event and serious adverse event monitoring.

Figure 1-1 Study design

2 First interpretable results (FIR)

Commercially Confidential Information

3 Interim analyses

Commercially Confidential Information

4 Statistical methods: Analysis sets

For patients for which the actual treatment received does not match the randomized treatment the treatment actually received will be used for the analysis.

The safety analysis set will include all patients that received any study drug.

The PK analysis set will include all patients with at least one available valid (i.e. not flagged for exclusion) PK concentration measurement, who received any study drug and experienced no protocol deviations with relevant impact on PK data.

The PD analysis set will include all patients with any available PD data, who received any study drug and experienced no protocol deviations with relevant impact on PD data.

For efficacy data summaries and statistical analyses for the Day 127 visit, only patients who have completed the treatment Epoch will be included. For Day 169, only patients who have completed the treatment Epoch and have completed the Follow-up Epoch will be included.

The analysis sets and protocol deviation codes are related as follows:

Table 4-1 Protocol deviation codes and analysis sets

Category	Text description of deviation	Data exclusion
Deviation code		
Patients are excluded from PK analysis in case of these PDs:		
INCL01	Written informed consent was not obtained before any study assessment was performed	Exclude patient from PK analysis set Yes
Patients are excluded from PD analysis in case of these PDs:		
INCL01	Written informed consent was not obtained before any study assessment was performed	Exclude patient from PD analysis set Yes
INCL3B	Patient did not fulfil the following: Tendinopathy with no more than a 50% tear as established by ultrasound at screening (historic data acceptable if not older than 3 months) and MRI at baseline: Sein MRI tendinopathy scoring system grade I-III; with no tear or partial tear [maximum 50% tendon thickness (Bauer tendon thickness score maximum 2); AP length maximum 10 mm (Bauer tendon length score max 2)]. Maximum 50% of patients with partial tear	Exclude patient from PD analysis set
INCL3C	Patient did not fulfil the following: Pain in the affected shoulder (at rest or on movement) on at least 3 days out of 7 days in the past week prior to baseline and a score of ≥4 out of 10 on a VAS pain scale	Exclude patient from PD analysis set
COMD02	Patient received prohibited concomitant medication	Exclude patient from PD analysis set
Patients are excluded from PK and PD analysis in case of these PDs:		
INCL01	Written informed consent was not obtained before any study assessment was performed	Exclude patient from PK and PD analysis sets Yes

5 Statistical methods for Pharmacokinetic (PK) parameters

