------------------------	--

Key Exclusion criteria	
 History of hypersensitivity to any of the study treatments or excipients or to drugs of similar chemical classes Rheumatologic, inflammatory diseases, including but not limited to: PsA, AS and RA Previous shoulder surgery in affected shoulder History of adhesive capsulitis/frozen shoulder or calcification in the tendon (in affected or contralateral shoulder) confirmed by X-Ray, historic X-Rays can be used if performed within 3 months of baseline Symptomatic osteoarthritis of the shoulder (gleno-humeral, acromioclavicular) (in affected or contralateral shoulder confirmed by X-Ray, historic X-Rays can be used if performed within 3 months of baseline) Neck conditions, including but not limited to cervical spine syndrome, which in the opinion of the investigator, may explain the patient's symptoms Previous platelet rich plasma injections within the last 12 months prior to randomization
Study treatment	
 Group 1: Secukinumab 300 mg s.c. (2 x 150 mg) Group 2: Placebo s.c. (2 injections)
Pharmacokinetic assessments	
 PK/immunogenicity assessment
Efficacy/PD assessments	
Patient Reported Outcomes (PROs)
 
 The WORC score The QuickDASH score The ASES score The EQ5D-5L score Patient's global assessment of disease activity 
Clinician Reported outcome
 
 Physician's global assessment of disease activity 
Imaging
 
 Shoulder MRI 
Commercially Confidential Information

Key safety assessments	
Key safety assessments:
 
 Evaluation of AE/ SAE's Physical examination Vital signs Height and weight Tuberculosis screening: QuantiFERON TB-Gold test or PPD skin test Chest X-Ray Electrocardiogram Local tolerability (Injection site reactions) Laboratory evaluations (Hematology, Clinical Chemistry, Lipid Panel, Urinalysis) Pregnancy and assessment of fertility 
Commercially Confidential Information
 
 Immunogenicity

Other assessments	Commercially Confidential Information

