8.1 Assessment schedule

Subjects should be seen for all visits/assessments as outlined in the assessment schedule, [Table 8-1](#), or as close to the designated day/time as possible.

Missed or rescheduled visits should not lead to automatic discontinuation. Subjects who prematurely discontinue the study for any reason should be scheduled for a visit as soon as possible, at which time all of the assessments listed for the final visit will be performed. At this final visit, all dispensed investigational product should be reconciled, and the adverse event and concomitant medications recorded on the CRE.

Table 8-1 Assessment schedule

Epoch	Screening			Treatment								Follow-up	
Visit Name	Screening	Run-in ²	Baseline	Treatment								Follow-up	EOS
Visit Numbers ¹	1	2	3	101	102	103	104	105	106	107	199	201	299
Days	-49 to -22	-21 to -8	-7 to -1	1	8	15	22 ±1	29 ±1	57 ±2	85 ±2	99 ±2	127 ±7	169 ±7
Weeks of dosing	-	-	-	0	1	2	3	4	8	12	14	18	24
Chest X-Ray ⁷			S										
Randomization				X									
Study drug administration ⁴				X	X	X	X	X	X	X	X		
Physiotherapy		S ¹³						S					
Physical Examination ⁵	S		S										S
Body Height ⁵	X												
Body Weight ⁵	X		X										X
Body Temperature ⁵	X		X	X		X		X	X	X	X		X
Blood Pressure and Pulse Rate ⁵	X		X	X		X		X	X	X	X		X
Electrocardiogram (ECG) ⁵	S		S									S	S
Hematology ⁵	X		X						X			X	X
Clinical Chemistry ⁵	X		X						X			X	X
Urinalysis ⁵	X		X									X	X
Lipid panel and glucose ⁵			X									X	
Shoulder X-Ray ^{6, 12}			S										
Shoulder US	S												
Shoulder MRI			X ¹²							X	X		X

Epoch	Screening			Treatment								Follow-up		
	Visit Name	Screening	Run-in ²	Baseline	Treatment								Follow-up	EOS
Visit Numbers ¹	1	2	3	101	102	103	104	105	106	107	199	201	299	
Days	-49 to -22	-21 to -8	-7 to -1	1	8	15	22 ±1	29 ±1	57 ±2	85 ±2	99 ±2	127 ±7	169 ±7	
Weeks of dosing	-	-	-	0	1	2	3	4	8	12	14	18	24	
PD blood (IL-17A) ⁵				X				X		X				X
Commercially Confidential Information														
PK blood collection ⁵					X				X		X			X
Commercially Confidential Information														
Immunogenicity ⁵					X							X		X
Commercially Confidential Information														
Concomitant medications												X		
Adverse Events												X		
Comments												X		
Study completion information														X

¹ Visit structure given for internal programming purpose only

² Run-in to standardize physiotherapy and stabilize NSAIDS, no site visit required

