11.1 Analysis sets

For all analysis sets, subjects will be analyzed according to the study treatment(s) received.

The safety analysis set will include all subjects that received any study drug.

The PK analysis set will include all subjects with at least one available valid (i.e. not flagged for exclusion) PK concentration measurement, who received any study drug and with no protocol deviations that impact on PK data.

The PD analysis set will include all subjects with available PD data and no protocol deviations with relevant impact on PD data.

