6.1.3 Statistical model, assumptions and hypotheses

The primary end-point (change from baseline in WORC score at Week 14) will be analyzed by repeated measures analysis of covariance including all WORC scores available. The change at Week 14 will be compared between treatments to address the primary objective.

The baseline WORC score will be included as a covariate. The stratification factors partial tear/no tear and previous steroid injection (yes/no) will be included in the model as fixed effects along with fixed effects for treatment, timepoint and the treatment by timepoint interaction. An unstructured within-patient covariance will be considered.

The number of covariance and mean parameters may be reduced by model comparison tools such as the BIC criterion for model fit. Missing variables will be considered missing at random.

The adjusted mean of treatment effect at Week 14 as well as the difference between treatment arms will be reported along with a 95% one-sided (90% two-sided) confidence interval.

The primary analysis will also be repeated for patients where the affected arm is the dominant arm.

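### The primary WORC analysis names no population and is not planned by randomized arm; a PD-set reading stays open and would drop patients for prohibited medication

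*SAP*

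**What the plan says.** **Grouping.** Protocol 11.1 states: "For all analysis sets, subjects will be analyzed according to the study treatment(s) received". SAP 4 agrees: "For patients for which the actual treatment received does not match the randomized treatment the treatment actually received will be used for the analysis". Both documents define three sets (safety, PK and PD). Neither defines a full or randomized set.

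**Primary analysis.** SAP 6.1.3 says that the Week 14 change in WORC "will be analyzed by repeated measures analysis of covariance including all WORC scores available". Protocol 11.4.2 says the same. Neither section names a set.

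**Efficacy rules by visit.** SAP 4 adds: "For efficacy data summaries and statistical analyses for the Day 127 visit, only patients who have completed the treatment Epoch will be included". It has a similar rule for Day 169 and none for Day 99, which is Week 14.

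**PD set.** In SAP 4 it holds treated patients with any PD data who "experienced no protocol deviations with relevant impact on PD data". Table 4-1 removes patients from it for code INCL3B (tear and MRI criterion), INCL3C (pain criterion) and COMD02, worded "Patient received prohibited concomitant medication". The COMD02 row removes the whole patient and gives no time window.

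**What PD means.** The protocol summary lists WORC and the other questionnaires under "Efficacy/PD assessments". The assessment schedule also contains a literal PD blood assay for IL-17A.

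**The concern.** The population for the primary test has to be inferred, and the two candidate populations behave differently.

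If all treated patients are used, no observed Week 14 score is lost. If the PD set is used, membership can depend on what a patient took after randomization. Taking a prohibited analgesic, or raising the NSAID or acetaminophen dose, is plausibly a response to poor pain control, and pain is close to what WORC measures. Such an exclusion would break the randomized comparison. The repeated-measures model, which assumes data missing at random, cannot recover a patient who has been removed altogether.

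Grouping by treatment received is a second, smaller departure from the randomized comparison. It matters only if someone receives the wrong treatment.

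**Working it through.** **1. Which population does the text support?**

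- For all treated patients: SAP 6.1.3 uses every available score, and SAP 4 restricts efficacy data only at Days 127 and 169. The IL-17A assay gives the PD set a purpose of its own.
- For the PD set: the protocol-summary heading pairs efficacy with PD. INCL3B and INCL3C are tear and pain entry criteria, and they act on the PD set only.

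The first reading is the stronger one. The second is not closed off.

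**2. Can a valid Week 14 score be deleted under the PD reading?** Yes, by a narrow route. Most rows of Protocol Table 5-1 call for stopping study medication. Protocol 7.2 then sends the patient to an early end-of-study visit, so many have no Week 14 score to lose. The exceptions are the NSAID/acetaminophen row and the other-analgesics row, which do not call for stopping study medication. Because COMD02 has no time window, a prohibited treatment after Week 14 could also remove an earlier score.

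**3. The plan's own power figure (Protocol 11.7).** SD = 22 × √(14/6) = 33.6, stated as 34. Effect size = 20/34 = 0.59. With 40 per arm and one-sided 0.05: 20/(34 × √(2/40)) = 2.63, and Φ(2.63 − 1.645) = 0.838 (0.832 by the t distribution). The claim of more than 80% is reproduced. With 50 per arm and no dropout, power is 0.899.

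**4. Illustration: one exclusion rule common to both arms.** The exclusion rates and slopes are assumed; the documents give none. Let y be the Week 14 change (higher is better), with mean 0 on placebo and 20 on secukinumab and SD 34. Let P(excluded | y) = Φ(a − b·y/34), with slope b = 0.5, 1 or 2.

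With ρ = b/√(1+b²), c = Φ⁻¹(1 − placebo rate) and h = c + ρμ/34, the fraction kept is Φ(h) and the mean of those kept is μ + 34ρ·φ(h)/Φ(h).

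Example with b = 1 and 10% of placebo excluded: ρ = 0.707 and c = 1.282.
- Placebo: 34 × 0.707 × 0.1755/0.900 = 4.69.
- Secukinumab: h = 1.282 + 0.707 × 0.588 = 1.698, so 4.5% are excluded and the mean is 20 + 34 × 0.707 × 0.0945/0.955 = 22.38.
- Estimate: 22.38 − 4.69 = 17.7.

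| Placebo excluded (assumed) | Secukinumab excluded, b = 0.5 / 1 / 2 | Estimate for a true 20 |
|---|---|---|
| 2% | 1.0 / 0.7 / 0.5% | 19.7 / 19.3 / 18.9 |
| 5% | 2.8 / 2.0 / 1.5% | 19.4 / 18.6 / 17.9 |
| 10% | 6.1 / 4.5 / 3.5% | 19.0 / 17.7 / 16.5 |
| 20% | 13.5 / 10.4 / 8.6% | 18.5 / 16.4 / 14.6 |

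Power from 50 per arm falls from 0.899 to 0.86-0.89 (2-5%), 0.82-0.86 (10%) or 0.74-0.82 (20%). From 40 per arm it falls from 0.832 to 0.78-0.82, 0.74-0.79 or 0.66-0.74. With no true effect, a common rule leaves the one-sided error at 0.05.

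**5. Illustration: unequal exclusion, no true effect.** Take 40 per arm, 20% against 10% of poor scorers excluded, and slopes 0.25 to 2. If secukinumab loses more, the bias is +1.3 to +4.7 points and the one-sided error 0.07 to 0.16. If placebo loses more, the bias is −1.3 to −4.7 and the error 0.04 to 0.01. The sign therefore depends on which arm loses more patients.

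**6. Grouping.** Suppose one patient in each arm of 50 gets the other treatment throughout and responds to what was received. Grouping by randomized arm gives 20 × (1 − 2/50) = 19.2, and grouping by treatment received gives 20. The two differ by 0.8 points.

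**7. What keeping the scores costs.** If prohibited medication adds r points to WORC, the full-set estimate is 20 − r × (placebo rate − secukinumab rate). With the 10% row it is 19.4-19.6 for r = 10 and 18.7-19.2 for r = 20. With the 20% row it is 18.9-19.3 and 17.7-18.7.

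**The case against.** The strongest reply is that nothing assigns WORC to the PD set and that the primary-analysis text points the other way. On the all-treated reading COMD02 deletes nothing, and what remains is an unnamed set and the grouping rule. That is correct. A reader might infer that the plan removes users of prohibited medication from the primary analysis; the documents do not say so.

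Other limits also stand:
- The set definition confines exclusions to deviations with a relevant impact on PD data. The COMD02 row does not repeat this, so it is unclear how automatic the exclusion would be.
- Table 4-1 may be broken. The INCL01 rows end in Yes and the COMD02 row does not, so a cell may be lost or a real difference intended.
- Protocol 11.4.3 and SAP 2 and 3 are redacted, and SAP 1.1 refers to other RAP documents. Any of these may hold related rules.
- The 10-20% rates and a slope of 2 (ρ = 0.89) are severe assumptions; at 2-5% the loss is modest. The calculation uses an unadjusted comparison, not the planned baseline-adjusted repeated-measures model.
- Unequal exclusion when the drug has no effect and the trial is blinded has no evident mechanism.

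What the reply does not remove is that the analysis-set and primary-model sections are readable, name no efficacy set, and group by treatment received.

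**Conclusion.** The concern holds in a limited form. The primary WORC comparison is not planned by randomized arm, and its population is not named. The text favours all treated patients but leaves open a PD-set reading under which COMD02 would remove whole patients, some with a valid Week 14 score, for an event plausibly related to outcome.

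The figures are illustrative and rest on assumed exclusion rates and an assumed link to the score. Under a common rule a true 20 becomes 17.9-19.7 at 2-5% placebo exclusion and 14.6-19.0 at 10-20%. The grouping rule is minor, at about 0.8 points per one swap each way per 50.

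A reader might also infer that the exclusion favours secukinumab or raises the false-positive rate. The documents do not support that. A common rule shrinks a true effect and leaves the error rate alone, and inflation needs a difference between arms for which the documents give no evidence.

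**What to change.** In SAP 4, define a full analysis set: all randomized patients who received any study drug, analysed by randomized arm, with every observed WORC score. Name it in SAP 6.1.3 and 6.2.4 as the primary efficacy set.

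Do not apply the COMD02 exclusion to the primary analysis. If a result without those patients is wanted, run it as supportive only and, for Week 14, count only deviations before Week 14. Keep treatment received for safety and PK.

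The cost is SAP wording and at most one extra run, with no new data. The downside is that the primary estimate then includes any effect of prohibited medication on WORC, which Protocol 3.2 wanted to avoid. The supportive analysis would show the result without those patients.
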